**Explanation:**

- |  |  |
|--|--|
| 
 
1 = No change (or condition has got worse)
 
2 = Almost the same, hardly any change at all
 
3 = A little better, but no noticeable change
 
4 = Somewhat better, but the change has not made any real difference
 
 | 
 
5 = Moderately better, and a slight but noticeable change
 
6 = Better, and a definite improvement that has made a real and worthwhile difference
 
7 = A great deal better, and a considerable improvement that has made all the difference
 
 |
|--|--|

Patient's signature: \_\_\_\_\_

**NOTE TO HEALTH CARE PROVIDER**

A significant, favorable change is a score of 5-7  
 No significant change is a 1-4 response.  
 Note, this a dichotomous scale (5-7 = yes; 1-4 = no).  
 A 2-point change is significant from their last reported score.  
 Reference: Hurst H, Bolton J. Assessing the clinical significance of change scores recorded on subjective outcome measures. *Journal of Manipulative Physiological Therapeutics (JMPT)* 2004;27:26-35.

Subject ID \_\_\_\_\_ Date (dd/mmm/yyyy): \_\_\_\_/\_\_\_\_/\_\_\_\_

[figure not shown]

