1. Inclusion/Exclusion, Registration, Medications, Treatment forms to be completed by site coordinator via online module.
2. Patient Onboarding and Orientation includes introductory demographics form, Nu-V3 patient training video
3. ePRO questionnaires completed on patient's mobile device: DQ-9 (baseline), PTB-7, PEG, GAD-7, PHQ-9, PROMIS 4a, PGIC
4. If patient consents to media testimony, site will collect via study collection process every 4 weeks.

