# Complete Patient ePRO Questionnaire Packet

Version Date: 07/Nov/2017

Approval Date:

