- Nu-Life reserves the right to capture video, photographs and written testimonials from patients with written permission. In the event subjects elect to participate in any or all of these activities, they will be asked to sign a waiver giving exclusive rights to the video, photographs and written testimonials captured to Nu-Life. Their participation in this study is not dependent upon their willingness to participate in video, photographs or written testimonials.

 Study Treatment Assessments Table 										
*Evaluations are completed weekly, every 7 days ≈3 days										
Evaluation*	Study Treatment									
	Week 1	Week 2	Week 3	Week 4	Week 5	Week 6	Week 7	Week 8	Week 9-11	Week 12
Informed Consent	x									
Inclusion and Exclusion ¹	x									
Patient Registration ¹	x									
Medications Form ¹	x			x				x		x
Patient Onboarding and Orientation ²	x									
In office assessment	x	x	x	x	x	x	x	x		x
New Device Placed	x		x		x		x			
Pad Replaced		x		x		x		x		
Treatment Forms ¹	x	x	x	x	x	x	x	x		
No Device									x	x
ePRO Questionnaires ³	x	x	x	x	x	x	x	x	x	x
Patients' Global Impression of Change ePRO form (PGIC) ³		x	x	x	x	x	x	x		x
Providers' Global Impression of Change ePRO form (PGIC)		x	x	x	x	x	x	x		x
Family Global Impression of Change ePRO form (PGIC)		x	x	x	x	x	x	x		x
Optional Patient Media Testimony	x			x				x		x

1. Inclusion/Exclusion, Registration, Medications, Treatment forms to be completed by site coordinator via online module.
2. Patient Onboarding and Orientation includes introductory demographics form, Nu-V3 patient training video
3. ePRO questionnaires completed on patient's mobile device: DQ-9 (baseline), PTB-7, PEG, GAD-7, PHQ-9, PROMIS 4a, PGIC
4. If patient consents to media testimony, site will collect via study collection process every 4 weeks.

Study Endpoints and Data Analysis: The study endpoints data were collected from each participant's study questionnaires. The data were collected electronically via the patient's own device, and were uploaded to an electronic data capture system. The data were used to demonstrate that the Nu-V3 device provides participants with relief of the symptoms of pain, depression, anxiety and/or sleeplessness. The data analysis includes comparative data for each participant's questionnaire prior to beginning treatment with the Nu-V3 device, the participant's weekly questionnaires during treatment and the questionnaire completed at the end of the treatment with the Nu-V3 device.

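### As printed, the PGIC form in the patient packet carries the provider's scoring key, and nothing in the plan says patients do not see it

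*Protocol*

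**What the plan says.** Protocol Section 8.1 and the SAP's Primary Endpoints both list the PGIC among the tools for primary effectiveness at 8 weeks, as the measure of overall quality-of-life improvement. The assessment table in Protocol Section 4.1 schedules it at Weeks 2 to 8 and at Week 12. Note 3 to that table reads "ePRO questionnaires completed on patient's mobile device: DQ-9 (baseline), PTB-7, PEG, GAD-7, PHQ-9, PROMIS 4a, PGIC", and the SAP's copy of the table carries the same note.

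The form is reproduced in Protocol Appendix 11, in a packet titled "Complete Patient ePRO Questionnaire Packet". It gives the question, the 1-7 scale, an explanation of each score and a line for the "Patient's signature". Below that comes a block headed "NOTE TO HEALTH CARE PROVIDER". The block states "A significant, favorable change is a score of 5-7" and "No significant change is a 1-4 response". It describes the scale as a yes/no split at that point, and adds that a 2-point move from the last reported score is significant. The packet holds no other copy of the patient PGIC. Neither document says that the block is removed, hidden or kept for staff.

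**The concern.** A patient-rated scale should not tell the rater which answers will be read as a good result. Here the key is part of the patient's form as printed, and the form is used repeatedly. A patient hesitating between 4 and 5 who has seen that 5 counts as significant has a reason to choose 5 that has nothing to do with their condition.

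The trial is single-arm and open-label, so an upward push on a subjective rating cannot be separated from device benefit. The SAP presents the study as the pivotal support for a De Novo request, which makes an avoidable source of rating bias on a primary tool worth removing.

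**Working it through.** No figure in the plan needs reproducing: neither document gives a power, alpha or effect-size statement for the PGIC. The check is a comparison of the texts, followed by a note on size.

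1. **Number of exposures.** From the PGIC row of the assessment table: Weeks 2 to 8 give 7 completions and Week 12 gives 1, so 7 + 1 = 8 through Week 12. A patient who reads the note only after signing at Week 2 still has 8 - 1 = 7 ratings to give. Six of those are at Weeks 3 to 8, the last being the primary time point. The remark about a 2-point move from the last score is a second cue on a form that is repeated weekly.

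2. **Practice elsewhere in the packet.** The PHQ-9 in Appendix 11 also addresses the healthcare professional, but it sends them to a separate scoring card and prints no cut-offs. Keeping the key off a patient form is therefore already done in this packet, and the PGIC departs from it.

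3. **Whether the plan uses 5-7.** Protocol Sections 8.1 and 8.2 and the SAP endpoints speak of median changes and statistically significant improvement. No PGIC responder rule appears in either document. The SAP's outcome template for quality of life leaves the measure type unselected, with both a count of participants and a median on offer. A 5-7 responder analysis is thus possible but not adopted, and the cut-off belongs to the form.

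4. **What the note adds to the scale's own wording.** The explanations above the signature line already describe 4 as a change of no real consequence and 5 as small but noticeable. A patient reading only those sees a step between 4 and 5. The note adds the label of significance and the yes/no split.

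5. **Size.** A shift in the proportion scoring 5-7 would be

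   shift = P(would answer 4) x P(moves to 5 because of the note).

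   The documents give neither term. As pure assumption, 20% (range 10-30%) and 25% (range 10-50%) give 0.20 x 0.25 = 5 percentage points, with a range from 0.10 x 0.10 = 1 to 0.30 x 0.50 = 15. The plan does not commit to analysing that proportion. The median it does mention would move only if it already lay at the 4/5 boundary. With a 5-point shift, the unprompted 5-7 proportion would have to be at least 45% and below 50%. These figures show how the bias would work and are not an estimate of it.

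**The case against.** The strongest reply is that exposure has not been shown. The block is addressed to the provider, it follows the signature line that closes the patient's part, and ratings are entered on a phone whose screens are not in the documents. Appendix 11 also looks like a set of source paper instruments: the PGIC asks for a number to be circled, the GAD-7 for column scores to be added, and the PHQ-9 for tick marks. The phone version may well omit the note.

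This stands as a limit on certainty: exposure on the phone is an inference. It does not dispose of the point. The packet is titled as the patient's electronic questionnaires, nothing instructs that the block be dropped, and the position below the signature line protects at most the first rating.

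Two further replies also stand in part. The plan's stated summary is a median, so a few answers moving from 4 to 5 would often leave it unchanged. And the explanations of scores 4 and 5, which should remain, already carry some of the same message, so any effect of the note alone is smaller than the effect of everything the form tells the patient about that step.

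**Conclusion.** The point holds in a limited form. As printed, the patient's PGIC includes the provider's scoring note, and the documents do not say that patients are spared it. Because the form is repeated through Week 12 in an open-label trial without a comparator, reading the note once could raise later ratings, including the one at Week 8. The size is unknown. The conclusion assumes that the phone version follows the printed form, which the sponsor can settle by showing the screen.

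A reader might infer that patients are shown the trial's success line while giving a primary rating. The documents do not support that. They contain no phone screen, and 5-7 is the form's own significance cut-off, whereas the plan's criterion is a statistically significant improvement with no PGIC threshold. Nor do they support a claim that the primary result is inflated by a given amount. The case for change is that a plausible source of bias on a primary tool can be removed at almost no cost.

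**What to change.** Delete the provider's note from the PGIC in the patient packet, so that the patient form stops at the scale, its explanations and the signature line. Confirm in writing that the phone version omits the note. Keep any scoring key in a separate site document, on the pattern of the PHQ-9 scoring card.

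If some patients have already used a form that showed the note, record which version each used and state this as a limitation. A comparison of Week 8 scores by form version would not help much: with 50-100 patients it would be small, and it would be confounded with calendar time.

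The cost is a re-versioned form with a new date and no new data. If the note does push ratings up, the PGIC result may be slightly less favourable without it.

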**Form PTB-7: Patient's Perceived Treatment Benefit**

[figure not shown]
For *initial assessment* of all symptoms, please rate your average symptom score prior to any treatment (i.e. over the last 30 days)

For any assessment *after treatment has been initiated*, please rate your global average symptom score since your last treatment

1. On a scale of 0-100%, how much benefit do you feel you have received from the Nu-V3 treatment in helping your symptoms?

2. How comfortable was the Nu-V3 device to wear?

3. Have you had any major discomfort from the device that has necessitated you to adjust the device placement?

\_\_\_\_ Yes  
\_\_\_\_ No

[figure not shown]
Subject ID \_\_\_\_\_ Date (dd/mmm/yyyy): \_\_\_\_/\_\_\_\_/\_\_\_\_

For *initial assessment* of all symptoms, please rate your average symptom score prior to any treatment (i.e. over the last 30 days)

[figure not shown]
For any assessment *after treatment has been initiated*, please rate your global average symptom score since your last treatment

4. Please rate your pain, anxiety, depression, and/or sleeplessness on a 0-10 scale:

[figure not shown]
Pain Level:

Anxiety Level:

Depression Level:

Sleeplessness Level:

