## 4.0 STUDY PROTOCOL

The Nu-V3 Clinical Study is a prospective, single-arm, open-label, multi-center study using the Nu-V3 cranial nerve stimulation treatment device in patients with pain, anxiety, depression, and/or sleeplessness.

For this Phase I study, a total of 50-100 patients at multiple centers will be registered for study participation. Study participants are those who have signed the informed consent form, met the inclusion and exclusion criteria, and are enrolled in the study at one of multiple sites. Enrolled participants are stratified based on their pain, anxiety, depression, and/or sleeplessness symptom presentation at baseline and treated with the Nu-V3 device for 8 weeks, then observed for an additional 4 weeks. Interim analysis of reported data will be based on baseline stratifications and conducted at 4, 8, and 12 weeks during this time. Post study, participants will be given the chance to continue with an optional maintenance treatment with the Nu-V3 device per a 2-weeks on, 2-weeks off schedule, for an additional 12 weeks, with an 8-week observation.

Subjects enrolled onto the Nu-V3 Clinical Trial will undergo the following regimen:

- At the baseline visit, patients will be asked to complete study questionnaires (Appendix 11) regarding all of the following symptoms: pain, anxiety, depression, and/or sleeplessness, as well as their quality of life, active medications, medical history, and demographical information.
- At each subsequent visit, patients will be asked to complete study questionnaires regarding all the following symptoms: pain, anxiety, depression, and/or sleeplessness, as well as their activity level and quality of life.
- The sessions will begin with the Nu-V3 device being placed on the left ear and three small pads (non-invasive) being placed on the ear. Each Nu-V3 device

lasts for up to 14 days with a change in the pads approximately 7 days into the treatment.

- Each session takes approximately 15-20 minutes. The placement of the device takes approximately 5 minutes and the remaining time is spent verifying ePRO form completion, and evaluating the patient for all device effects.
- The Nu-V3 device is mobile and is worn externally on the left ear 24 hours a day during treatment, fitting comfortably behind the ear. An electrical signal is sent to the external ear through coated wire leads attached to the device and adhesive pads which attach to three sites on the ear.

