## 5.0 DATA COLLECTION AND RETENTION

The study endpoints data will be collected from each participant's study questionnaires. The data will be collected electronically via the patient's own device, and uploaded to an electronic data capture system. Only patient data from the stratified indication(s) will be used for analysis of symptom response. The data will be used to demonstrate that the Nu-V3 device provides participants with relief of the symptoms of pain, depression, anxiety and/or sleeplessness. The data analysis will include comparative data for each participant's questionnaire prior to beginning treatment with the Nu-V3 device, the participant's weekly questionnaires during

treatment and the questionnaire completed at the end of the treatment with the Nu-V3 device.

Interim analyses of available data will be regularly submitted to the FDA for review.

The Principal Investigator at each site will be responsible for recording, collecting, and storing the research participant's study data. The written records must be stored in a secure location. Only the Principal Investigator or designated study staff will have access to the study records and all electronic files will be password protected. The Principal Investigator will also maintain adequate records for the study including:

- all correspondence with the IRB and Sponsor
- other pertinent data related to the study

All records are to be retained by the Principal Investigator for a period of seven (7) years following the closure of the study. Following study closure, the Principal Investigator shall inform Nu-Life of the location of study records and storage changes (i.e. the Principal Investigator leaves the institution where the study was conducted). In such cases, the study records may be transferred to another institution, investigator, or to Nu-Life upon written agreement between the Principal Investigator and Nu-Life.

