## 8.0 STUDY ENDPOINT and DATA ANALYSIS

### 8.1 Primary Endpoints: Primary endpoints consisted of the following:

Safety: The primary safety endpoint is the occurrence of reported unanticipated problems involving risk to subjects or others (“UPIRTSOs”). These UPIRTSOs are defined as those problems which alter the risks to subjects or others. This includes any study suspensions or holds. The primary safety endpoint analyses will be based on a risk-benefit conclusion.

Effectiveness: The primary effectiveness endpoints are an overall change in median reported symptoms of pain, anxiety, depression, and/or sleeplessness via numeric rating scales at 8 weeks. This primary effectiveness is measured by median reported symptom changes in pain, anxiety, depression, and/or sleeplessness for respective stratified populations via the following validated tools: Pain - Pain Intensity and Interference (PEG\_Scale), Anxiety - Generalized Anxiety Disorder 7-item (GAD-7) scale, Depression - Patient Health Questionnaire (PHQ-9), Sleeplessness - PROMIS short form 4a, and overall improvement of quality of life (QOL) - Patient’s Global Impression of Change (PGIC).

The hypothesis-driven criterion of effectiveness is to show that there is a statistically significant reduction in the median reported pain, anxiety, depression, and/or sleeplessness levels of patients using the Nu-V3 device. The second criterion is intended to show that there is a statistically significant improvement in reported quality of life and perceived treatment benefit, secondary to overall reported symptom reductions of pain, anxiety, depression, and/or sleeplessness.

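### PTB-7 item 4 uses a 30-day recall window at baseline and an undefined one afterwards, so change from baseline on these 0-10 ratings can partly reflect the window

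*Protocol*

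**What the plan says.** Form PTB-7 (Protocol, Appendix 11) gives two recall instructions. For the initial assessment: "please rate your average symptom score prior to any treatment (i.e. over the last 30 days". For any assessment after treatment has begun: "please rate your global average symptom score since your last treatment". Both are printed twice on the form, the second time around item 4, which reads: "Please rate your pain, anxiety, depression, and/or sleeplessness on a 0-10 scale".

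PTB-7 belongs to the ePRO set in Protocol section 4.1. That set is completed at Week 1, weekly to Week 8, and in the off-device period to Week 12. Section 4.0 says the device is "worn externally on the left ear 24 hours a day during treatment".

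Section 8.1 describes the primary effectiveness endpoint as "overall change in median reported symptoms of pain, anxiety, depression, and/or sleeplessness via numeric rating scales at 8 weeks". The next sentence says the endpoint is measured "for respective stratified populations via the following validated tools: Pain - Pain Intensity and Interference", and goes on to GAD-7, PHQ-9, PROMIS 4a and PGIC. PTB-7 is not on that list. Protocol section 8.2 and the SAP's Primary Endpoints section both describe PTB-7 as a non-validated effectiveness tool for perceived benefit and device comfort. Neither document says whether or how the item 4 ratings are analysed.

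**The concern.** Section 5.0 sets out a before-after comparison: "The data analysis will include comparative data for each" participant's questionnaire before treatment against the weekly and end-of-treatment questionnaires. On item 4 those two sets of answers refer to periods of different length, and the switch falls exactly at the boundary between baseline and treatment. The study has one arm, so no control group goes through the same switch, and an effect of the window cannot be told apart from an effect of the device.

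This matters only if item 4 enters an effectiveness claim, and the documents leave three routes open. First, sections 8.1 and 8.2 and the SAP refer to numeric rating scales, and item 4 is the only 0-10 rating in the packet that covers all four symptoms. Second, the SAP places PTB-7 under the primary endpoints. Third, the sub-analyses of weeks of sustained response and weeks to initial benefit (Protocol 8.3, repeated in the SAP) name no instrument.

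**Working it through.** The documents give no effect size, SD, alpha or power for this point, so there is no plan figure to reproduce.

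**1. Recall windows and scales, from the forms in Appendix 11**

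| Form | Scale | Baseline window | Later window |
|---|---|---|---|
| PTB-7 item 4 | 0-10, all four symptoms | 30 days | since last treatment |
| PEG | 0-10, pain only | 1 week | 1 week |
| GAD-7 | items 0-3, anxiety | 2 weeks | 2 weeks |
| PHQ-9 | items 0-3, depression | 2 weeks | 2 weeks |
| PROMIS 4a | five verbal categories, sleep | 7 days | 7 days |

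Of these symptom measures, only PTB-7 changes its window.

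**2. How long the later window is**

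Inputs from section 4.1: new device at Weeks 1, 3, 5 and 7; pads replaced at Weeks 2, 4, 6 and 8; no device in Weeks 9-12. Take the visit in week w as day 7 x (w - 1), ignoring the visit tolerance. Week 7 is then day 42, Week 8 is day 49, the end of Week 8 is day 56 and Week 12 is day 77.

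- Last treatment read as the last visit or pad change: 7 days at each of Weeks 2-8; 77 - 49 = 28 days at Week 12.
- Read as the last new device: 7 days at Weeks 2, 4, 6 and 8; 14 days at Weeks 3, 5 and 7; 77 - 42 = 35 days at Week 12.
- Read as the end of wear: no elapsed time while the device is on; 77 - 56 = 21 days at Week 12.

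Setting aside the zero-length reading, the window is 30 days at baseline, 7-14 days on treatment and 21-35 days at Week 12.

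**3. What this can do to one patient (invented scores, no device effect)**

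- Score 8 for 23 days, then 5 for the week before Week 1 and after: baseline (8 x 23 + 5 x 7)/30 = 7.3. Week 2 over 7 days is 5. Apparent fall 7.3 - 5 = 2.3.
- Score 5 for 23 days, then 8 for the week before Week 1 and after: baseline (5 x 23 + 8 x 7)/30 = 5.7. Week 2 is 8. Apparent rise 8 - 5.7 = 2.3.
- With a 7-day window at both times, the change is 0 in both cases.

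**4. What a net shift would do to a test (all inputs assumed)**

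Let d be a mean shift due to the window alone, with true change 0, a two-sided 5% level and a one-sample normal test on paired change:

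P(significant) = Phi(d x sqrt(n)/SD - 1.96) + Phi(-d x sqrt(n)/SD - 1.96)

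The sample sizes are the ends of the planned 50-100 range. The SD of change runs from 3.0 to 2.0.

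| d | n = 50 | n = 100 |
|---|---|---|
| 0 | 5% | 5% |
| 0.25 | 9.1-14.3% | 13.3-24.0% |
| 0.5 | 21.8-42.4% | 38.5-70.5% |
| 1.0 | 65.4-94.2% | 91.5-99.9% |

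For example, d = 0.5, n = 50, SD = 2.0: 0.5 x sqrt(50)/2.0 = 1.768, and Phi(1.768 - 1.96) = 0.424; the second term is negligible.

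**The case against.** The strongest reply is that item 4 has no stated analytic use. A reader might infer from the reference to numeric rating scales that the primary endpoint rests on these ratings. The documents do not support that: the sentence directly after it in section 8.1 names the measures, PTB-7 is not among them, and PEG is itself a 0-10 scale. Nor does either document plan to use item 4 as a check on PEG or PROMIS 4a. This part of the reply stands and limits the reach of the point.

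A reader might also infer that the mismatch flatters the device. That is not shown either. The two cases in step 3 go in opposite directions. If symptoms are stable and recalled averages are unbiased, the window length alters the variance of the rating and leaves its expected value unchanged. The exclusion of patients with medication changes in the last 60 days makes treatment-driven shifts before baseline less likely.

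The third objection is to the remedy. Take a patient at 5 who flares to 8 in the week before enrolment and returns to 5. The 30-day baseline is 5.7, an apparent fall of 0.7. A 7-day baseline is 8, an apparent fall of 3.0. A long baseline window damps regression to the mean and a short one does not. That is correct and belongs among the costs.

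Finally, some figures on PTB-7 are not shown in the text available, so further wording on the printed scales cannot be ruled out.

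What remains is that four symptom ratings are collected at baseline and weekly, on a form both documents call an effectiveness tool, under instructions that make the two sets non-comparable, and nothing in the plan keeps them out of effectiveness claims.

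**Conclusion.** The point holds for PTB-7 item 4 and no further. Change from baseline on these ratings can partly reflect a move from a 30-day window to one of about 7-14 days on treatment and about 21-35 days at Week 12, the later figures depending on how last treatment is read. The direction is unknown and the documents give no basis for a size.

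The 2.3-point figures show what is possible in one invented patient. The rejection rates in step 4 depend wholly on the assumed shift and SD: an assumed 0.5-point net shift with 50 patients would raise a nominal 5% error rate to about 22-42%, and a net shift of zero would leave it at 5%. PEG, GAD-7, PHQ-9 and PROMIS 4a, and any primary result based on them, are untouched. This is worth correcting because it is cheap and because the plan leaves the role of item 4 open.

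**What to change.** - Print one fixed recall window on every PTB-7 administration, from Week 1 through the off-device weeks, in all places where the two instructions appear. The past 7 days is one choice: it fits the weekly visits and matches PEG and PROMIS 4a, though not the 2-week windows of GAD-7 and PHQ-9.
- In Protocol 8.1 ("via numeric rating scales at 8 weeks"), the matching phrase in 8.2, and both endpoint sections of the SAP, replace the reference to numeric rating scales with the named validated tools.
- State in both documents that item 4 is exploratory, and that ratings taken under mismatched windows do not count toward effectiveness or toward the response and time-to-benefit sub-analyses.

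The cost is an edit to the ePRO instructions (each of the two lines is printed twice) and short text changes in the two documents. There are two real downsides. Baselines already collected over 30 days cannot be compared with ratings under the new window. A 7-day baseline is also more exposed to regression to the mean if patients enrol during a flare, and a common window does nothing to remove that in a single-arm study.
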